14.0 Risks to Subjects

14.1 Reasonably foreseeable risks, discomforts, hazards, or inconveniences related to participation in the research.

Phase 1. Potential risks are considered minimal. There are some potential minimal psychological risks associated with participation in the interviews, intervention development sessions and answering some of the intervention development questionnaires. However, participants will be given the option to not answer or skip any questions that make them feel uncomfortable. Further, although the research team will take every precaution to maintain confidentiality of the data, the nature of some web-based sessions prevent the researchers from guaranteeing confidentiality. The research team will be sure to reiterate this risk during all group sessions and remind participants to respect the privacy of your fellow participants and not repeat what is said in these sessions to others.

For the app field study, participants may increase their PA compared to their usual level of PA, although they will be explicitly told this is not the purpose of the field test. Engaging in a PA program when one has been sedentary for a considerable period of time incurs some risk of injury such as muscle soreness, strains, aggravation of arthritic conditions, etc. However, serious physical injury is considered unlikely. Participants will be instructed to notify study investigators immediately if they experience any adverse effects of using the app.

PROTOCOL TITLE: Designing with Dissemination in Mind: Optimization of a mHealth Physical Activity Intervention for Breast Cancer Survivors (Fit2Thrive)

For the app field study, there is also a small risk to individuals' privacy when using the mHealth app. However, this will be minimized by the procedures described, above. Participants are permitted to refuse to participate in any aspect of the research and may withdraw from the study at any point, for any reason without penalty.

Phase 2. Potential risks are considered minimal. Engaging in a PA program when one has been sedentary for a considerable period of time incurs some risk of injury such as muscle soreness, strains, aggravation of arthritic conditions, etc. However, serious physical injury is considered unlikely. In order to reduce and/or prevent any physical harm or injury subjects will gradually increase their PA. Additionally, each participant will be required to pass a screening test or receive medical approval prior to enrollment to ensure PA is appropriate. Furthermore, all participants, regardless of the intervention components they receive, will be provided access to a study website that is also embedded within the app which will include an overview of safety issues and stress the need to contact study investigators should they experience any adverse effects of PA. Finally, the intervention content will emphasize safety and present instruction to reflect safe progressions.

In addition to the potential minimal risk associated with PA participation, there are some potential minimal psychological risks associated with answering some of the questionnaires required for participation in this study. However, participants will be given the option to skip any questions that make them feel uncomfortable. Should any individuals report scores on the PROMIS Cancer Depression Scale, that are in the 75th percentile (i.e. ≥ 4.3) or confer a high level of distress in interactions with research study staff, they will be referred to American Psychosocial Oncology Society (APOS) Toll-Free HELPLINE - [name] ([name]). We have chosen this method because women will be selected from all over the United States. APOS's Helpline is a national resource to help people with cancer and their caregivers find emotional support in their own communities. This is a referral program that is part of the Cancer Support Helpline® (affiliated with the Cancer Support Community) and connects cancer patients, their caregivers and advocacy organizations with psychiatrists, psychologists, nurses, social workers, and counselors skilled in the management of cancer-related distress. If Helpline counselors cannot find local support services, and there is an immediate need for help, a Helpline mental health counselor can provide short-term emotional support by phone while patients seek professional help with coping in their community. Calls are accepted Mon-Fri 9 am- 8 pm ET.

There is also a small risk to individuals' privacy when using the mHealth app but this will be minimized by the procedures described, above.

Finally, for those participating in the optional blood sample collection, pricking the finger for the blood sample may cause some minor discomfort. Additionally, the risks of taking blood include pain, a bruise at the point where the blood is taken, redness and swelling of the collection site and infection, and a rare risk of fainting. The risk of fainting could be elevated if a participant is already feeling faint or dizzy. They will be instructed to delay collecting the blood sample until they are feeling better if this is the case.

Participants are permitted to refuse to participate in any aspect of the research and may withdraw from the study at any point, for any reason without penalty.

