PROMIS Physical Function Short Form 20a.¹⁰⁵ The PROMIS Physical Function Short Form 20a will be used to assess participants' physical function. The scale has two subscale limitations and interference. For the 6 limitations items, participants will rate the level of difficulty they have had executing discrete activities over the past 7 days on a scale from 1 (unable to do) to 5 (without any difficulty). For the 4 limitations items, patients will rate the degree to which their health limits them in specific activities on a scale from 1 (cannot do) to 5 (not at all). Higher scores reflect better physical function. The reliability of this measure ranges from $\alpha=0.90$ to $\alpha=0.95$.¹⁰⁶

PROMIS Fatigue Short Form 8a.¹⁰⁵ The PROMIS Fatigue Short Form 8a will be used to assess participants' frequency of fatigue symptoms ranging from 1 (not at all) to 5 (very much) and fatigue interference ranging from 1 (never) to 5 (always) over the past 7 days. Higher scores reflect higher levels of fatigue. The reliability of this measure ranges from $\alpha=0.90$ to $\alpha=0.95$.¹⁰⁶

PROMIS Sleep Disturbance Short Form 8a.¹⁰⁵ The PROMIS Sleep Disturbance Short Form 8a will be used to assess participants' rating of overall sleep quality from 1 (very good) to 5 (very poor) and perceptions of specific characteristics of sleep quality on a scale ranging from 1 (not at all) to 5 (very much). Higher scores reflect higher levels of sleep disturbance. The reliability of this measure ranges from $\alpha=0.90$ to $\alpha=0.95$.¹⁰⁶

PROMIS Depression Short Form 8a.¹⁰⁵ Participants are asked to indicate the frequency of a variety of depressive symptoms over the past 7 days on a 5 point scale from 1 (never) to 5 (always). Higher scores reflect higher depressive symptoms. The reliability of this measure ranges from $\alpha=0.90$ to $\alpha=0.95$.¹⁰⁶

PROMIS Sleep-Related Impairment Short Form 8a.¹⁰⁵ The PROMIS Sleep –Related Impairment Disturbance Short Form 8a will be used to assess participants' perceptions or sleep-related impairment on a scale ranging from 1 (not at all) to 5 (very much). Higher scores reflect higher levels of sleep-related impairment. The reliability of this measure ranges from $\alpha=0.90$ to $\alpha=0.95$.¹⁰⁶

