*Exercise Goal-setting Scale.*¹¹¹ This 10-item scale will assess participants exercise-related goal-setting, self-monitoring and problem solving and instructs participants to indicate the extent to which each of the statements describes them on a scale from 1 (does not describe) to 6 (describes completely). This scale has demonstrated good internal consistency ($\alpha= 0.89$).¹¹¹

*Multidimensional Outcome Expectations for Exercise Scale.*¹¹² This scale will assess participants' social (4 items), self-evaluative (5 items), and physical (6 items) outcome expectations for exercise participation on a 5 point scale ranging from 1 (strongly disagree) to 5 (strongly agree). The three subscales have demonstrated good internal consistency ($\alpha= 0.82$ for physical outcome expectations, $\alpha= 0.81$ for social outcome expectations, and $\alpha= 0.84$ for self-evaluative outcome expectations).¹¹²

*Physical Activity Enjoyment Scale.*¹¹³ This 18-item scale will assess the degree to which participants, at the current moment, enjoy doing any sort of physical activity. This 18-item scale rates enjoyment on a 7-point bipolar scale ("It makes me depressed"..."It makes me happy"). This measure has demonstrated good internal consistency in previous studies ($\alpha= 0.93$ to $\alpha= 0.96$).¹¹³

PROTOCOL TITLE: Designing with Dissemination in Mind: Optimization of a mHealth Physical Activity Intervention for Breast Cancer Survivors (Fit2Thrive)

Table 6. Schedule of Measures					
	Screening	Baseline	3 weeks	12 weeks	24 weeks
Physical Activity Readiness Questionnaire	X				
Mobile Device Proficiency Questionnaire		X			
Demographics		X			
Breast Cancer History		X		X	X
Health History		X		X	X
Actigraph Accelerometer		X		X	X
Godin Leisure Time Exercise Questionnaire-Current		X	X	X	X
Godin Leisure Time Exercise Questionnaire-Before diagnosis		X			
Sitting Time Questionnaire		X		X	X
PROMIS Physical Function Short Form 20a		X		X	X
PROMIS Fatigue Short Form 8a		X		X	X
PROMIS Depression Short Form 8a		X		X	X
PROMIS Anxiety Short Form 8a		X		X	X
PROMIS Emotional Support Short Form 8a		X		X	X
PROMIS Sleep Disturbance Short Form 8a		X		X	X
PROMIS Sleep-Related Impairment Short Form 8a		X		X	X
Rosenberg Self-Esteem Scale		X		X	X
Physical Self-Perception Profile Physical Self-worth Subscale		X		X	X
Physical Activity Neighborhood Environment Survey		X			
Exercise Self-efficacy Scale		X	X	X	X
Barriers Self-efficacy Scale		X	X	X	X
Social Support for Exercise Scale		X	X	X	X

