23.0 Number of Subjects

PROTOCOL TITLE: Designing with Dissemination in Mind: Optimization of a mHealth Physical Activity Intervention for Breast Cancer Survivors (Fit2Thrive)

23.1 Total Number of Subjects to be accrued.

A total of 356 breast cancer survivors, 30 other stakeholders and 128 “buddies” will be accrued.

Phase 1. In phase 1, we plan to recruit breast cancer survivors up to 100 breast cancer survivors, a subgroup (n=30) will participate in interviews and the full sample (n=100) has the potential to participate in the app development sessions and field test. A total of 20-30 experts (n=10-15) (n=10-15) will be recruited for interviews.

Phase 2. For the pilot intervention, we will accrue 256 breast cancer survivors. Approximately 50% of these will be assigned to the buddy condition. As such we will accrue 128 buddies. We anticipate 80% of these “buddies” (n=102) will agree to participate in the optional questionnaire assessments. For the post-intervention interviews, we plan to accrue up to 35 women.

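### The score-based depression referral trigger of 4.3 cannot be applied consistently with the depression instrument that the protocol describes and schedules

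*Combined protocol and SAP*

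**What the plan says.** Section 14.1, under Phase 2, sends a woman to a national cancer helpline on either of two grounds. The first is a questionnaire score: "scores on the PROMIS Cancer Depression Scale, that are in the 75th percentile (i.e. ≥ 4.3"). The second is joined by an or, and covers women who show strong distress to staff: "or confer a high level of distress in interactions with research study staff".

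The depression questionnaire in Section 9.4 has a different name, "PROMIS Depression Short Form 8a". Its items are rated "on a 5 point scale from 1 (never) to 5 (always). Higher scores reflect higher depressive symptoms". Table 6 schedules that form at baseline, 12 weeks and 24 weeks, and no other depression instrument appears in it.

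The documents do not state the number of items on the form, how items are combined into a score, the population behind the percentile, or whether the two names mean the same scale. The Phase 2 sample is given in Section 23.1: "For the pilot intervention, we will accrue 256 breast cancer survivors".

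**The concern.** A referral threshold has meaning only on a stated metric. Here the number, its percentile label and the instrument do not fit together on the readings that can be checked. Summing the items puts 4.3 below the lowest possible score. Averaging them puts 4.3 close to the top of the range, which is a strange place for a 75th percentile.

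What is at stake is how distress is handled, not the efficacy analysis. This is the only score-based distress trigger in the protocol. Two staff members following Section 14.1 could take opposite actions on the same completed form.

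The staff-observed trigger does not fully cover the gap in a remote trial. Support calls go only to women randomised to that component, and only in the first 12 weeks (Section 9.2, Intervention Components). Regular staff contact ends at week 12 (Section 9.2, Follow-up). The eight-weekly adverse event enquiry runs through week 24, but it asks about health and medical problems and can be completed by RedCap form (Section 9.2, safety monitoring for Phase 2). At the 24-week assessment, the score may be the main route to referral for many women.

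**Working it through.** **Inputs**

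- Cut-off: 4.3 or more, labelled the 75th percentile (Section 14.1).
- Item range: 1 to 5, higher meaning more symptoms (Section 9.4).
- Number of items: 8, assumed from the form's name, because no section states it.
- Women in Phase 2: 256 (Section 23.1).
- Mean and SD of the score: not in the documents, so a range is used below.

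The plan's own figure, 4.3 as a 75th percentile, cannot be reproduced, because no scoring rule, reference population, mean or SD is given.

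**Reading 1: sum of items**

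- Minimum 8 × 1 = 8; maximum 8 × 5 = 40.
- The minimum of 8 exceeds 4.3, so every woman who completes the form is flagged.
- This does not depend on there being eight items. Any sum over five or more answered items is at least 5, which also exceeds 4.3.

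**Reading 2: mean of items**

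- The range is 1 to 5, so 4.3 can be reached.
- Sum required: 4.3 × 8 = 34.4, so 35 or more. A sum of 34 gives 34/8 = 4.25 (not flagged); 35 gives 35/8 = 4.375 (flagged).
- Of the 33 attainable sums (8 to 40), 6 are flagged (35 to 40). The other 27 are flagged under Reading 1 but not under Reading 2.
- A woman answering 4 on every item has a mean of 4.0 and is not flagged by score, whatever the number of items.

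**Does the percentile label fit Reading 2?**

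For a normal distribution, the 75th percentile is mean + 0.6745 × SD. Setting it to 4.3 and solving for the reference-group mean:

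- SD 0.6: 4.3 − 0.6745 × 0.6 = 3.90
- SD 0.8: 4.3 − 0.6745 × 0.8 = 3.76
- SD 1.0: 4.3 − 0.6745 × 1.0 = 3.63

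So a typical member of the reference group would have to average about 3.6 to 3.9 out of 5 on depressive symptoms. If the trial sample matched that group, 0.25 × 256 = 64 women would be flagged.

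**Share flagged under Reading 2, for assumed distributions**

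The table gives the percentage with a mean item score above 34.5/8 = 4.3125 (halfway between sums of 34 and 35). Each cell shows a normal distribution first, then a beta distribution scaled to 1 to 5.

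| Assumed mean | SD 0.6 | SD 0.8 | SD 1.0 |
|---|---|---|---|
| 1.5 | 0.00 / 0.08 | 0.02 / 1.22 | 0.25 / 4.50 |
| 2.0 | 0.01 / 0.03 | 0.19 / 0.67 | 1.04 / 3.20 |
| 2.5 | 0.13 / 0.11 | 1.17 / 1.40 | 3.50 / 5.04 |
| 3.0 | 1.44 / 0.99 | 5.04 / 5.01 | 9.47 / 11.45 |

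For means of 1.5 to 2.5 this is about 0% to 5% (0 to 13 of 256). For a mean of 3.0 it is about 1% to 11% (3 to 29 of 256).

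**Reading 3: standardised z-score**

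The 75th percentile of a standard normal variable is about 0.67, not 4.3.

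**The case against.** The strongest reply is that 4.3 lies inside the 1 to 5 response range, so an item-mean reading makes the cut-off attainable and is the more natural one. That stands: it would be wrong to say that the number cannot fit the scale. It does not explain the percentile label, however, and no section says that items are averaged.

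The eight items are also an inference. Section 9.4 describes the Physical Function form labelled 20a as 6 plus 4 items, so the labels in this text are not dependable item counts. This affects the figures of 35 and 40. It does not affect the result for sums of five or more items, or the woman who answers 4 throughout.

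The mismatch in names may be loose wording. The reference cited for the depression form is a paper on PROMIS-Cancer scales in advanced-stage cancer patients. That makes it plausible that one instrument is meant. Whether the 4.3 or its percentile comes from that paper cannot be checked here. If it does, the reference group differs from this trial's, which takes Stage I to III disease and excludes metastatic disease.

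A reader might infer that the safety rule flags either every woman or almost none. The documents do not support that. The first half needs summing, which no section states. The second half needs a score distribution, which no section gives; the percentile wording itself implies about a quarter of the reference group. The staff-observed distress trigger also operates regardless of the score. Section 14.1 does not say when scores are reviewed, so nothing can be claimed about referral at every assessment.

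Finally, the action is a helpline referral, and the threshold enters no endpoint, model or sample size. That limits the weight of the point without removing it.

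**Conclusion.** The point holds as an internal inconsistency between Section 14.1 and Section 9.4 with Table 6. No calculation in the protocol is wrong. A decision threshold is stated without a metric, under an instrument name that the measures section does not use, and with a percentile label that fits none of the three readings examined.

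The firm results are these. Under summing, all women who complete the form are flagged, for any form of five or more items. Under averaging, a woman answering 4 on every item is not flagged by score. The remaining figures are conditional: a sum of at least 35 of 40 assumes eight items; a reference mean of 3.6 to 3.9 assumes normality and an SD of 1.0 to 0.6; the shares flagged rest on the assumed means and SDs and are illustrations, not predictions.

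Only the score-based trigger is affected. It deserves correction because it is the only one of its kind and regular staff contact stops at week 12.

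**What to change.** Reconcile Section 9.4, Table 6 and Section 14.1 so that they:

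- name one depression instrument throughout;
- state the score metric that the trigger uses (sum, item mean or standardised score), and how it is computed when items are skipped, since Sections 9.3 and 14.1 let women decline questions;
- name the population from which the percentile is taken;
- express the cut-off on that metric.

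The choice of cut-off belongs to the clinical team, and none is proposed here. Any alert in RedCap or elsewhere that has been programmed with 4.3 should be checked against the corrected text. The cost is a short protocol correction and that check; the design, sample size and outcome analyses do not change.

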15.0 Potential Benefits to Subjects

Phase 1. The benefits of this portion of the study are largely scientific. Participants will have the benefit of contributing to the advancement of science by contributing to the development of a mHealth intervention for breast cancer survivors. This information is crucial to the effective development and implementation of the PA intervention to be tested in Phase 2.

Phase 2. Although not guaranteed, the potential benefits of participating in this study include improved cardiorespiratory fitness, physical functioning, quality of life, depression and fatigue. All participants will be able to participate in the program for free. This study has the potential to inform science by improving the understanding of how to promote PA in breast cancer survivors, a large, and growing population with many health concerns. Additionally, the approach used to develop the intervention has the potential to be applied to other areas of science to facilitate the efficiency by which research can be disseminated into practice. We believe that the minimal risk involved with study participation are reasonable in relation to the anticipated benefits.

16.0 Vulnerable Populations

N/A

17.0 Community-Based Participatory Research

17.1 Involvement of the community in the design and conduct of the research.

Stakeholders including local, Chicago-area breast cancer survivors and representatives from relevant Chicago-area and national cancer organizations will be involved in designing and choosing the intervention components to be tested as part of Phase 1 of this study.

18.0 Sharing of Results with Subjects

Phase 1. Women who participate in this portion of the study will have the option of selecting to receive a plain language study summary at the end of Phase 1 and to indicate whether they would like to receive any manuscripts that result from Phase 1 or Phase 2 of the present study. All women who indicate they would like to receive either the plain language summary or have manuscripts shared with them, will be e-mailed final versions of any manuscripts that result from the data upon publication in peer-reviewed journals. These manuscripts will also be posted on the PI's website which study participants will have access to.

Phase 2. Results will be shared with subjects via a plain-language study summary that will be sent via e-mail to participants at the conclusion of all data collection and cleaning. Women will also be given the option to indicate they would like manuscripts that are

PROTOCOL TITLE: Designing with Dissemination in Mind: Optimization of a mHealth Physical Activity Intervention for Breast Cancer Survivors (Fit2Thrive)

published as a result of these data to be shared with them. All women who indicate they would like to have manuscripts shared with them, will be e-mailed final versions of any manuscripts that results from the data upon publication in peer-reviewed journals. These manuscripts will also be posted on the PI's website which study participants will have access to.

19.0 Setting

19.1 Sites or locations where research will be conducted.

Phase 1. Recruitment. Breast cancer survivors will be recruited from the Lynn Sage Breast Cancer Program at RHLCC using pamphlets/fliers and physician referrals. Fliers and pamphlets will also be posted in the local community, sent to listservs and posted on social media and on-line forums. Additionally, the PI will send a recruitment e-mail to an existing database of breast cancer survivors. Community representatives will be recruited in conjunction with NU's Center for Community Health (led by Co-I [name]) via personalized e-mails and phone calls. Experts will be recruited through the RHLCCC and the PI's, co-investigators' professional networks via listservs and personalized e-mails and phone calls. **Research Procedures:** All research procedures will be performed in the Department of Preventive Medicine, [name].

Phase 2. Recruitment: Our main source of recruitment will be e-blasts sent to women registered with the Army of Women.[©] Other recruitment sources will include posting on on-line forums and websites, RHLCC, and fliers distributed at local community organizations and events. **Research Procedures:** All research procedures will be performed in the Department of Preventive Medicine, [name].

We are confident sample recruitment through the Army of Women[©] is feasible, based on my prior experience recruiting and retaining a much larger sample. In our prior study, we had 2,500 women express interest within 12 hours of recruitment initiation and recruitment was halted due to capacity limitations. Of that number, 1,631 (64%) responded to screening and qualified to participate. I randomized 500 of those women to wear accelerometers for 7 consecutive days. Only 4 refused to wear the device. At baseline and follow-up, 1,527 women (94%) completed more than half of the on-line questionnaires. Valid accelerometer data were obtained from 442 (89%) women at baseline; 370 (83.7%) of those women also had valid data at 6 month follow-up. Reasons for missing accelerometer data at baseline and follow-up, respectively, were: did not wear ($n=36$ and $n=40$), insufficient valid wear time ($n=8$ and $n=17$), accelerometer malfunctioned ($n=5$ at both), lost in mail or by participant ($n=4$ and $n=5$) and submerged in water ($n=1$).

If we are not able to sufficiently meet our recruitment goals using the Army of Women[©], additional NU resources (e.g. RHLCC and the Center for Community Health), on-line

PROTOCOL TITLE: Designing with Dissemination in Mind: Optimization of a mHealth Physical Activity Intervention for Breast Cancer Survivors (Fit2Thrive)

forums and social media sites (i.e. Facebook, the Sisters Network and Nueva Vida) and fliers at community organizations and events will be used.

Percentage of PI's Effort Dedicated to Project. The PI will dedicate approximately 60-80% of her effort to this project during data collection and between 30-40% during data analyses.

Facilities. Phase 1 will be conducted in the Department of Preventive Medicine in private conference rooms or using the Northwestern University's IT services (for web-based conferences). Phase 2 will be conducted via a mobile app. All data from this will be stored on a secure, password protected server that will only be accessible to study investigators.

Process to Ensure all Staff are Adequately Informed on Protocol. All staff with access to the data will have completed Northwestern University requirements for the responsible conduct of research including the Collaborative Institutional Training Initiative (CITI) Training Modules. A manual of procedures will be developed for the current project which will include scripts for any contact research staff will have with study participants. The PI will meet with the research assistant (TBD) from the Department of Preventive Medicine to train them in these procedures. Additionally, the PI will meet with the RA on a weekly basis, and as needed, to ensure study procedures are being adhered to.

